This pilot study will determine the tolerance and anti-tumor efficacy of irradiated haploidentical blood mononuclear cells (irradiated allogeneic cells, IAC) in patients with high-risk hematologic malignancies who have undergone autologous or allogeneic hematopoietic stem cell therapy. There will be 2 cohorts:

-Cohort 1 will be composed of patients with high-risk non-Hodgkin lymphoma or multiple myeloma; they will have undergone high dose chemotherapy with *autologous* stem cell rescue but remain at high risk for relapse.

-Cohort 2 will be composed of patients with high-risk hematologic malignancies who have undergone an HLA-matched *allogeneic* hematopoietic stem cell transplant. The IAC will be administered either prophylactically (for those identified to be at high risk at the time of transplant) or after molecular, immunophenotypic or clinical relapse (if the patient is not a candidate for standard donor lymphocyte infusion or alternate standard therapy).

- **Primary Objective**

The primary objective is to determine the toxicity associated with the administration of IAC to patients with high-risk hematologic malignancies.

- **Secondary Objective**

To secondary objective is to determine if there is evidence of disease response associated with IAC. This will be determined by standard disease staging, use of minimal residual disease markers, and/or by clinical analysis by the Hematologic Malignancies Tumor Study Group as directed by disease and disease state.

- **Tertiary Objective**

To determine if treatment with the irradiated cells induces an immune response targeting tumor associated epitopes.

Hypotheses

-An "allogeneic effect" (enhancement of an immune reaction by the presence of a concurrent allogeneic reaction) has been demonstrated in animal studies, is operative in humans and, can be used to enhance anti-tumor responses (1-6).

-Treatment with IAC, as done previously at ██████████ will induce an "allogeneic effect" that results in a clinical anti-tumor response (6,7).

- IAC induce the production of T cells that target tumor associated epitopes (7).

Primary Endpoint(s)

- Determine the toxicities associated with administration of IAC. The anticipated/projected IAC-associated toxicities of greatest concern include:
 - Short-term toxicities: constitutional/systemic adverse events including fevers, hypotension, pulmonary infiltrates;
 - Long-term toxicities: autoimmune effects, graft-versus-host disease (GVHD), graft rejection;

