Registration: Once a potential donor has been identified for respective patient, both the patient / recipient and the relative/ donor will sign consent to participate in the study. Upon signing the consent, donor will undergo protocol mandated screening for eligibility. Once donor's eligibility is confirmed both patient and donors will be registered for the study by OHRS research staff.

Each participant will be given a unique identifier code. No patient will start treatment prior to registration.

All eligible patients will be treated at [REDACTED] and receive standard treatment per Blood & Marrow Transplant Program Policies.

1. Patients in cohort 1 will be treated initially with IAC within 42 days after hematopoietic engraftment (both neutrophils and platelets). Engraftment is

defined by 3 consecutive measurements with absolute neutrophil count > 500/mm³ and platelets > 20,000/mm³ without transfusion.

2. Patients in cohort 2 with *high-risk* disease will be treated initially with IAC within 120 days after hematopoietic engraftment (neutrophils and platelets). Chimerism studies must reveal engraftment of donor CD3+ cells > 80% and there must not be any evidence of > grade I *acute* GVHD or *severe* chronic GVHD, per standard CIBMTR staging.
3. Patients in cohort 2 being treated for *relapsed* disease may receive initial treatment with irradiated allogeneic cells any time after relapse documented. They may receive disease specific therapy prior to the experimental cell therapy, but they must have recovered from the disease-specific therapy prior to the experimental cell therapy.
4. All treated patients who do not have evidence of relapse or progressive disease may be treated q 8-12 weeks for up to 3 treatments with delays up to 8 weeks as clinically indicated.
5. Donor will undergo evaluation at RWJ Blood Services within 7 days of each infusion.
6. Donors meeting eligibility requirements will be harvested by leukapheresis with targeted CD3+ (0.5-3.0 x 10⁸/kg); harvesting will be done according to FACT and AABB guidelines.
7. Donor cells (0.5-3 x 10⁸ CD3+/kg) will be irradiated (25 Gy) and infused no more than 24 hours after harvesting of the cells; in case of ABO incompatibility either RBC depletion will be undertaken or the product will be split to assure infusion of \leq 10 ml ABO incompatible RBC/day.
8. Management of cytopenias, infections, and other complications will conform to standard procedures at the discretion of the physician.

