If there is (1) a steroid refractory GVHD or (2) graft failure in cohort 2, then the study will stop.

The secondary aim is to determine if there is evidence of disease response to IAC. If there is evidence of disease response in either arm, additional studies will be planned.

f) Study Variables

• *Independent Variables or Interventions*

IAC infusion every 8-12 weeks as tolerated and feasible.

Toxicity will be measured by occurrence of any experimental treatment-related Adverse Events (AE) up to 12 weeks of completion of therapy. The CTCAE Version 4.0 will be utilized for the description and grading of the AE. All symptoms, signs, or diseases assessed as experimental treatment-related will be captured and graded by a study investigator and an attribution will be associated to the experimental therapy (IAC).

Attribution of the AE:

- Definite – The AE is clearly related to the experimental therapy
- Probable – The AE is likely related to the experimental therapy
- Possible – The AE may be related to the study treatment
- Unlikely – The AE is doubtfully related to the study treatment
- Unrelated – The AE is clearly NOT related to the study treatment

Any experimental treatment-related irreversible grade 3 or higher AE (definite, probable or possible) will result in that patient not receiving any further treatment. If the AE corrects completely or to Grade 1 within 2 weeks, repeat treatment as directed by protocol may be utilized. If there is more than one such irreversible experimental treatment-related Grade 3 adverse event, the study will be terminated for that cohort.

Since a major concern is that the IAC might trigger an immune response that results in steroid-refractory GVHD OR graft failure (in cohort 2), specific parameters to diminish the likelihood of these events are included in the inclusion criteria (e.g. durable engraftment and high donor chimerism). Furthermore, the study will be terminated if even a single episode of these events occurs.

Overall response rate will be defined as the proportion of patients meeting the criteria for partial response (PR), very good partial response (VGPR) and complete response (CR). Disease response will be determined by Standards of Blood and Marrow Transplant Program disease-specific parameters.

- *Dependent Variables or Outcome Measures*

Toxicity and disease response will be measured. Disease response will use standard disease-specific parameters.

g) Drugs/Devices/Biologics

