Irradiated allogeneic cells are administered under a FDA awarded IND.

h) Primary Specimen Collection

-Standard disease monitoring q 3 months

-Immunologic studies immediately prior first infusion and 30 days after each IAC infusion; if no additional infusions administered samples will be obtained also at day +60 and day +90. No samples will be repeated within 21 days of each other.

i) Interviews, Focus Groups, or Surveys

N/A

- *Administration*

N/A

- *Study Instruments*

Standard policies and procedures of the Hematologic Malignancies and Blood & Marrow Transplant Programs of Rutgers Cancer Institute of New Jersey

Timetable/Schedule of Events: Patients and donors will be consented when they meet eligibility criteria, up to 90 days prior to anticipated first treatment. Patients and donors will be registered in ONCORE within 7 days of anticipated first treatment.

Patient Procedures	Screening (within 14 days of registration- unless otherwise noted)	Pre each cycle of IAC (- 7 days)	Q 30 days (+/- 7 days) after each IAC infusion ⁶	Completion of therapy (within 8 weeks of last protocol treatment and monitoring)
Informed Consent ¹	X			
Inclusion/Exclusion	X			
Hx, PE, ECOG Performance Status	X	X	X	X
Toxicity Assessment	X	X	X	X
Hematologic and Biochemical Profile ²	X	X	X	X
Serum Pregnancy Test (if of childbearing potential)	X	X		
Disease staging BMasp/biopsy ³	X		X	
HLA and ABO/Rh Typing	X			
Infectious Disease Screening ⁴	X	X		
Ancillary studies: immune function ⁵	X	X ⁷	X	X

1. Patients will be consented within 90 days of anticipated first treatment with irradiated cells.
2. Standard CBC, chemistry profile
3. Disease staging as clinically indicated per standards of Blood & Marrow Transplant Program
4. Infection Disease Screening per RWJ transplant services within 7 days of harvesting.
5. For patients for whom there is a disease specific epitope that can be monitored during therapy four tubes of EDTA anticoagulated blood will be collected at each time point and sent to the Immune Laboratory. No need to wait for results. These patients will be identified at baseline evaluation for collection beginning prior to 1st cycle of IAC.
6. These assessments will be performed Q 30 days until the patient receives their next IAC infusion, completes protocol therapy or comes off study.
7. No need to repeat if prior sample drawn within 21 days.

Donor Procedures	Screening	Within 7 days of each donor leukapheresis	Day of Collection

[REDACTED]

10

RESERVED FOR IRB STAMP

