- Patients undergoing haploidentical allogeneic hematopoietic stem cell transplants are not eligible; patients undergoing < 10/10 HLA allele matched allogeneic transplant are not eligible
- Pregnant women
- Children are not eligible as the transplant program is certified as an adult only transplant program.

(5) Subject Screening - DONOR

(a) Inclusion Criteria - DONOR

- Donor must be related to patient and be partially ($\geq 3/6$ antigen) HLA-matched.
- Donor must meet all RWJ Blood Services requirements for hematopoietic stem cell donation including:
 - Age ≥ 18 years old;
 - normal hemogram (WBC $4.0-10.0 \times 10^3/\text{mm}^3$; platelet count 150,000 to $440,000/\text{mm}^3$; Hemoglobin/Hematocrit; 12.5-18 g/dl, 38 to 54%)
 - not pregnant or lactating;
 - not HIV-1, HIV-2, HCV, Hepatitis B core or HTLV-I/II seropositive; HB S ag (-); meet other infectious disease screening criteria utilized by RWJ Blood Services;
 - no uncontrolled infections, other medical or psychological/social conditions, or medications that might increase the likelihood of patient or donor adverse effects or poor outcomes;
 - meet other blood bank criteria for blood product donation (as determined by RWJ Blood Center screening history and laboratory studies).
- Male and female and all ethnic groups are eligible provided they are fluent in English.

(b) Exclusion Criteria

- Non-English speaking person
- Pregnant women
- Children are not eligible as the transplant program is certified as an adult only transplant program.

(6) Recruitment Materials

N/A

(7) Lead Site Recruitment Methods

N/A

- **Subject Randomization**

N/A

- **Secondary Subjects**

N/A

- **Number of Subjects**

- (1) Total Number of Subjects**

A total of 20 subjects will complete the study. There will be 10 patients in each cohort. There will be a donor corresponding to each patient. There may be additional potential; donors screened if a donor fails the screening.

- (2) Total Number of Subjects If Multicenter Study**

N/A

- (3) Require Number of Subjects to Complete Research**

The number of subjects needed to complete the research procedures (i.e., numbers of subjects excluding screen failures.) is 40 (twenty patients and twenty donors). Each patient will participate in the study for 3 infusions and then be followed until disease progression or 3 years. Patients will be enrolled over a 3 year period of time.

- (4) Feasibility Of Recruiting**

We expect to enroll 7 subjects per year onto this study.

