The infusion of irradiated cells may be associated with short-term effects such as fevers, chills, dyspnea and systemic inflammatory symptoms such as shortness of breath due to pneumonia or diarrhea due to colitis. Long-term effects may include infection or autoimmunity. For patients who have received an allogeneic transplant the manifestation of "autoimmunity" might be graft-versus host disease or graft rejection.

(b) Risk Of Imposing An Intervention On Subject With Existing Condition

N/A

(c) Other Foreseeable Risks

The patients receiving therapy with IAC have very high-risk diseases and are receiving IAC as an adjuvant to transplant therapy. It may be hard to determine the toxicity related to their disease, standard treatment (transplant therapy) or the experimental therapy (IAC). In this context all patients will be at risk for infection, bleeding, organ toxicity (including heart, lung, kidney, liver, oropharyngeal, gastrointestinal, neurologic, ophthalmic and bone marrow) some of which might be irreversible and some of which could lead to long-term morbidity and death. These risks are intrinsic to the disease and standard therapy and may be worsened by the experimental therapy.

(d) Observation And Sensitive Information

N/A

(5) Minimizing Risks

The experimental intervention (IAC) involves administration of irradiated Patients receiving IAC will be reviewed weekly at 2 meetings – a weekly transplant meeting and a weekly clinical research meeting. Any SAE considered likely related to IAC will be discussed and presented for biometric evaluation re:stopping rules.

(6) Certificate of Confidentiality

N/A

(7) Potential Benefits to Subjects

IAC may improve clinical outcomes by increasing disease response rates and disease control.

(8) Provisions to Protect the Privacy Interests of Subjects

Patient confidentiality will be strictly maintained according to NIH guidelines.

(a) Research Team Access To Subject Data

The subject's personal health information, identifiers and research data are stored and kept in a secure area in the [REDACTED] computer screens containing personal health identifiers are inaccessible to public view. Only the study doctor and research team will have direct access.

c) Secondary Data – Records/Chart Reviews/Databases/Tissue Banks/etc.

[REDACTED]

20

RESERVED FOR IRB STAMP
DO NOT MODIFY THIS SPACE

Form V

Approval Date:
Expiration Date:

4/23/2021
4/22/2022

N/A

Chart/Record Review Selection

N/A

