- **Secondary Specimen Collection**

Blood samples for immune studies will be frozen immediately prior to each infusion and at 30, 60 and 90 days following infusions if there is not a sample drawn within 21 days as part of pre-infusion sampling.

5) Special Considerations

d) Health Insurance Portability and Accountability Act (HIPAA)

Protected Health Information (PHI) under HIPAA means any information that identifies an individual and relates to at least one of the following:

- The individual's past, present or future physical or mental health
- The provision of health care to the individual
- The past, present or future payment for health care

Health information related to this study may be used or disclosed in connection with this research study, including, but not limited to, information in the patient medical record such as certain information indicating or relating to a particular medical condition, blood and other tissue samples and related records, physical examinations, x-rays, MRI's, etc. Personal identity, such as a name, address, and other identifiers, will be kept confidential.

Patient information will only be used in accordance with permission by the subject (IRB approved signed informed consent form) as required or allowed by law.

e) Family Educational Rights and Privacy Act (FERPA)

N/A

f) NJ Access to Medical Research Act

N/A

g) Code of Federal Regulations Title 45 Part 46 (Vulnerable Populations)

N/A

- **"Special" Classes Of Subjects**

N/A

6) Research Data Protection and Reporting

a) Data Management and Confidentiality

Data will be collected as per the standard Bone Marrow Transplant procedures and research data will be stored in Oncore. Data will be analyzed by the PI. Patients participating in this study will have real-time data obtained from the Blood & Marrow Transplant Program weekly research meeting AND the weekly clinical research meeting of the Hematologic Malignancies Tumor Study Group. Additional data will be obtained from data forms for submission to the Center for International Bone Marrow Transplantation Registry (CIBMTR) as part of a separate IRB-approved protocol. If a patient participating in this study does not agree to have data collected for submission to the CIBMTR, data will be collected by the Investigator from the electronic medical record.

b) Data Security

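### Long-term toxicities named in the primary endpoint are counted only to 12 weeks after therapy, so later-starting events do not enter the toxicity result

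*Combined protocol and SAP*

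**What the plan says.** The Primary Endpoint(s) section makes toxicity of the irradiated cells a primary endpoint and separates short-term from long-term concerns. The second group reads "Long-term toxicities: autoimmune effects, graft-versus-host disease (GVHD), graft rejection". The section on reasonably foreseeable risks repeats the idea: "Long-term effects may include infection or autoimmunity". It adds that after an allogeneic transplant this might appear as GVHD or graft rejection.

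Section f) Study Variables gives the one operational definition, for all toxicity alike: "Toxicity will be measured by occurrence of any experimental treatment-related Adverse Events (AE) up to 12 weeks of completion of therapy".

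The Timetable/Schedule of Events marks toxicity assessment at screening, before each cycle, every 30 days after an infusion, and at a final visit headed "Completion of therapy (within 8 weeks of last protocol treatment and monitoring)". Footnote 6 ends the 30-day assessments at the next infusion, at completion of protocol therapy or when the patient leaves the study.

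On treatment length, item 4 of the Treatment Plan says that patients without relapse or progression "may be treated q 8-12 weeks for up to 3 treatments with delays up to 8 weeks as clinically indicated". On follow-up, the section on the required number of subjects says: "Each patient will participate in the study for 3 infusions and then be followed until disease progression or 3 years".

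Section e) Sample Size Justification/Statistical Analysis sets 10 patients per cohort. It claims 80% or better assurance that the true unacceptable rate lies under 30%, and closes the study if a cohort has more than one irreversible treatment-related event of grade 3 or higher. Sections e) and f) also stop the study for a single steroid-refractory GVHD or graft failure in cohort 2, with no time limit stated.

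**The concern.** The endpoint and its measurement cover different periods. The plan names three toxicities as long-term, then counts them over the same window as a fever after infusion. No separate definition, window or analysis is given for them, and no toxicity assessment is scheduled in later follow-up.

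If the plan is followed exactly, a late autoimmune disorder or late chronic GVHD attributed to the cells can occur while the patient is still under study follow-up and yet not enter the primary toxicity result. A report of acceptable tolerance could then be taken as covering long-term toxicity when the data behind it stop at 12 weeks after therapy.

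**Working it through.** **1. The plan's own figure.** Inputs from section e): n = 10 per cohort, unacceptable rate 30%, at most 1 event tolerated. Confidence that the rate is below 30% after x events is 1 − P(X ≤ x | n = 10, p = 0.30).

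- x = 0: 1 − 0.7^10 = 1 − 0.028 = 97.2%. The one-sided 80% upper limit is 1 − 0.2^(1/10) = 14.9%.
- x = 1: 1 − (0.7^10 + 10 × 0.3 × 0.7^9) = 1 − (0.028 + 0.121) = 85.1%. The exact one-sided 80% upper limit is 27.1%.

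Both exceed 80%, so the stated assurance reproduces. It describes events that are counted, and the only counting rule given is the 12-week window.

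**2. When the window closes.** Inputs: up to 3 infusions, 8 to 12 weeks apart, delays up to 8 weeks (Treatment Plan, item 4), and 12 weeks after completion (section f). I take completion to mean the last infusion, because the plan does not define it for patients who stop early. For three infusions, last infusion = 2 × (interval + delay), and close = last infusion + 12.

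| Course | Last infusion (week) | Window closes (week after first infusion) |
|---|---|---|
| One infusion | 0 | 12 |
| Three, every 8 weeks | 16 | 28 |
| Three, every 12 weeks | 24 | 36 |
| Three, every 12 weeks plus 8-week delay each time | 40 | 52 |

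**3. Follow-up outside the window.** The maximum is 3 years = 156 weeks. The plan does not say clearly where the 3 years start.

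- Counted from the last infusion: 156 − 12 = 144 weeks, or 92%.
- Counted from the first infusion, three infusions: 156 − 28 = 128 (82%), 156 − 36 = 120 (77%), 156 − 52 = 104 (67%).

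These are upper bounds, because follow-up ends at progression.

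**4. The schedule against the window.** If the final visit falls within 8 weeks of the last infusion and the 30-day assessments have ended, no toxicity assessment is scheduled for the remaining 4 weeks of the 12-week window, and none after it.

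**5. How much late onset the 80%/30% statement could absorb if read without a time limit.** Let f be the share of unacceptable events that start after the window. The documents give no value for f, so I solve for the break-even. The implied all-time upper limit is (in-window limit)/(1 − f), which reaches 30% at f = 1 − limit/0.30.

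- With 1 of 10 seen: 1 − 0.271/0.30 = about 10%.
- With 0 of 10 seen: 1 − 0.1487/0.30 = about 50%.

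This does not estimate how many late events there will be. It shows that at the tolerated limit of 1 in 10 there is little room for any.

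**The case against.** The best reply is that a limited window is defensible and that safeguards continue beyond it. The cohort 2 stopping rule has no time limit, the closure rule in section e) states no window of its own, and cumulative safety review is weekly with no end date. The earlier study cited in the background reported no GVHD with irradiated cells. The risk section admits that toxicity of the cells is hard to separate from disease and transplant effects, and in a single-arm pilot of 10 per cohort late GVHD has no comparator.

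Much of this stands, and it limits the point. A reader might infer that a cohort could be called tolerable despite any late graft event. The documents do not support that for cohort 2, where a late graft failure or steroid-refractory GVHD could still stop the study. What remains uncovered is autoimmunity, GVHD that is not steroid-refractory, and cohort 1. A stopping rule or a weekly meeting also does not place late events in the reported toxicity measure. On irradiation, section f) itself fears that the cells might provoke GVHD or graft failure through an immune response.

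A reader might also infer that events about six months into treatment are missed. For a patient given three infusions, week 26 after the first infusion lies inside the window, which closes at week 28 at the earliest. What is lost is onset more than 12 weeks after the last infusion.

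**Conclusion.** The concern holds as a mismatch between the endpoint and its measurement. Named long-term toxicities that start more than 12 weeks after the last infusion do not enter the toxicity result. The window closes at week 28 to 52 after the first infusion for a full course and at about week 12 after a single infusion, against follow-up of at most 156 weeks. The 80%/30% statement is correct for events inside the window and says nothing about later ones.

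This rests on reading completion of therapy as the last infusion and on section f) being the only definition of toxicity. Actual follow-up may be far shorter than 3 years. It ends at progression, the background section projects disease-free survival under 25% in cohort 2, and the plan gives a study duration of 3 years alongside enrolment over 3 years.

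Three stronger readings are not supported:

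- That long-term safety makes up a fixed share of the primary endpoint. The lists are anticipated concerns, and disease response appears under the primary endpoints too.
- That a particular proportion of late events will be missed. The documents give no onset times.
- That the plan promises a 3-year safety conclusion. It never defines long-term.

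**What to change.** Reconcile the Primary Endpoint(s) section, section f), the schedule of events and the follow-up statement.

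1. Keep the 12-week window for all adverse events. Describe that result, including the 80%/30% statement, as tolerance to 12 weeks after therapy. Say what completion means for patients who stop early, and align the final toxicity assessment with the window.
2. For autoimmune effects, GVHD and graft rejection, record, grade and attribute events during the follow-up already planned. Sources are clinic records and the registry forms that section 6(a) already foresees ("Additional data will be obtained from data forms for submission to the Center for International Bone Marrow Transplantation Registry (CIBMTR)"), with the medical record as the fallback that the same section provides for patients who decline registry submission.
3. Report these events as a named long-term component of the primary endpoint, with each patient's follow-up time.

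No treatment rule, stopping rule or sample size changes. The cost is protocol wording and some added abstraction, grading and attribution, since no toxicity assessment is now scheduled in that period. Whether the registry forms capture autoimmune events cannot be seen from the documents and should be checked. The long-term component will read out later, attribution without a comparator will be harder, and follow-up will be short for patients who progress or enrol late.
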